
• 5 minutes: Welcome• 5 minutes: Review of goals from prior week• 10 minutes: Review of food and/or activity tracking• 15 minutes: New weekly topic• 20 minutes: Set SMART* goals for the following week• 5 minutes: Positive reflections 
*Specific Measureable Achievable Relevant Timely
	
1. My Plate; SMART goal setting; Food tracking2. My Plate: fruits and vegetables; Weigh-ins; Activity tracking3. Triggers for over-eating; Mindful eating4. Sugars in food and beverages; How to be physically active5. Fats; Healthy cooking strategies6. Importance of physical activity7. Social support8. Stress eating; Mindful eating9. Loss of control; Managing problem foods; Social eating situations10. Planning healthy meals11. Self-compassion with eating12. How to keep going long term
Group Session Goals	Group Session Strategies

• Reduction of portion size (My Plate)• Shift of relative dietary content to My Plate proportions (i.e., 50% fruits and vegetables)• 150 minutes per week of moderate to vigorous physical activity• 10,000 steps per day	
• Food records• Physical activity trackers• Weight monitoring• SMART goal setting• Feedback and re-enforcement• Modeling and social support• Problem solving• Self-efficacy enhancement

Intervention guide. The study team, with RHCP community partners, has developed an intervention guide that will be printed and made available on the RHCP web site and within the program leader space on WellConnect. The guide consists of 3 sections: Section 1 includes the 12 content modules. Section 2 includes principles of facilitating evidence-based cognitive-behavioral techniques for healthy behaviors: goal setting, feedback/reinforcement, self-efficacy enhancement, modeling, and problem solving.¹³⁷ Section 3 includes a list of low or no cost community resources for physical activity and healthful eating.

The programmatic intervention dose is lower than many health promotion interventions. The rationale is that 1) the intervention will be more impactful when delivered by a member of participant's social network,¹³⁸ and 2) non-programmatic health promoting activities and interactions are likely to occur within and between social networks (indirect intervention effect) throughout the study interval.¹³⁹ This approach highlights the potential advantages of social network interventions for scalability and sustainability.^{70,140}

The rationale for the mentorship and education component of the intervention arose from the success of this model in the Healthy Immigrant Families study, where the interventionists were not necessarily members of participant's social networks. For this application, mentorship has the potential to carry more influence through

delivery within social networks by respected peers. Peer mentoring has been shown to be effective in promotion of healthy eating and physical activity among groups with low socioeconomic position.^{141,142}

Treatment Fidelity & Measures

Treatment Fidelity

In the design and conduct of this study, we have incorporated recommendations from the Treatment Fidelity Workgroup.¹⁴³ We have recently described our process for assessing treatment fidelity for community-based behavior change interventions with immigrant groups in a CBPR framework.¹³⁶ The HPs will utilize a manual (phase 1) containing an outline/script for each session and a checklist of critical topics to be covered at each session. Study assistants, who were interventionists for the Healthy Immigrant Families study, will randomly observe 5% of sessions with the HPs. These study assistants have developed expertise as health behavior change interventionists through 250 hours of training followed by two years of intervention delivery.¹³⁶ They will be further trained in fidelity assessment for this study, thereby addressing the barrier of language concordance between interventionists and assessors. Bi-weekly meetings will be held with the HPs and study team to reinforce treatment fidelity, provide corrective feedback, and to conduct additional training if needed.

Measures

Data will be collected at 0 (baseline), 6, 12 (primary endpoint) and 24 months by trained study staff blinded to treatment condition. Participants will complete a survey and participate in physical measurements.

Demographic, acculturation, and structural racism measures. The following demographic data will be collected at baseline: age, gender, ethnicity, country of birth, annual household income, education level, employment status, and use of social media. Participants will report on the following proxies for acculturation: years lived in the US, primary language spoken at home, and level of English language proficiency on a 5-point Likert scale.¹⁴⁴ Degree of dietary acculturation¹⁴⁵ will be assessed from results of 24-hour dietary recall described below. The following measures of structural racism will be obtained at baseline: Home address for automated collection of geolocation-based measures (Minnesota Measure of Structural Racism [MMSR], Area Deprivation Index [ADI], County Structural Racism Index); Everyday Racism Scale, Discrimination in Medical Settings Scale, and Medical Mistrust Scale.

Primary outcome measures.

BMI: Weight will be measured to the nearest 0.1 kg using a portable scale (Seca 880 Digital Floor Scale). Height will be measured to the nearest 0.1 cm at baseline only using a stadiometer. Participants will be asked to remove shoes prior to both measurements. BMI is calculated as weight (kg)/height squared (m²). Waist circumference will be measured to the nearest 0.1 cm at the narrowest part of the torso between the ribs and the iliac crest. Participants will remove excess clothing prior to the measurement and smooth the remaining clothing against the skin. Two measurements will be taken; if the difference between the two measures is more than 2.0 cm, a third measurement will be taken. The average of the two closest measures will be used.

Secondary outcome measures. The secondary outcome measure will be the "Life's Simple 7" Composite Score, which is adapted from the American Heart Association standards based on health assessment data¹⁴⁶: average blood pressure from 3 readings, fasting lipid panel and glucose, height, weight, self-reported cigarette smoking status, dietary quality, and physical activity patterns). Point values are assigned to each component: 2 points for ideal, 1 point for intermediate, 0 points for poor. The total sum allows for a continuous measure of cardiovascular health ranging from poor to ideal (0-14 points). The final score will be categorized as 0-6 (poor), 7-8 (intermediate), 9-14 (ideal). In previous studies, adherence to the ideal Life's Simple 7 metrics was found to be associated with decreased risks of cardiovascular disease¹⁴⁷ and all-cause mortality¹⁴⁸.

Seated blood pressure (systolic and diastolic) measurements will be made on the right arm using an automated BP Tru BPM-200 after sitting quietly for five minutes.¹⁴⁹ Blood pressure will be measured three times and the average of the second and third readings will be used in analyses. Fasting glucose and cholesterol will be collected by a single finger prick obtained by Mayo Clinic CRU staff. Participants will be asked to refrain from eating for at least 6 hours prior to testing. The portable Whole Blood Lipid Screen Cholestech LDX Analyzer will

be used to analyze specimens, which combines enzymatic methodology and solid-phase technology measured by reflectance photometry to measure total cholesterol, HDL cholesterol, triglycerides and glucose in whole blood. LDL cholesterol is a calculated value. Samples used for testing are whole blood from a fingerstick collected in a lithium heparin coated capillary tube. Results will be recorded at the site of collection and samples will be destroyed upon recording of results.

Dietary Quality: Two 24-hour dietary recalls will be collected using the Automated Self-administered 24-hour Recall (ASA24) system, a National Cancer Institute web-based tool that enables multiple automated self-administered 24-hour recalls. The recalls will be performed using a computer under the supervision of study staff. The tool is available in English and Spanish. A study staff member and an interpreter will complete the recall with participants who speak other languages. Through these intake estimates, the effect of the intervention on diet quality (Healthy Eating Index plus intake of fruits, vegetables, sweetened beverages, percent energy from fat and total calorie consumption) may be examined.

Physical activity: The International Physical Activity Questionnaire (IPAQ)¹⁵⁶ will be used to assess the number of minutes of mild, moderate, and vigorous physical activity over the previous 7 days. We have used objective measures of physical activity in past studies (accelerometers) as a primary outcome,⁴⁴ but for this study the survey will be used only to observe changes over time, not as an objective measure of activity.

Table 4. Life's Simple 7 domains and derivation of its composite score¹⁵⁷⁻¹⁵⁹

“Life’s Simple 7” Domain	Optimal (2 points)	Intermediate (1 point)	Poor (0 points)
Weight	BM<25	BMI 25-29.9	BMI ≥30
Blood pressure	SBP<120 and DBP<80	SBP 120-139 and DBP 80-89	SBP≥140 or DBP≥90
Total cholesterol	<200 mg/dL	200-239 mg/dL	≥240 mg/dL
Fasting glucose	<100 mg/dL	100-125 mg/dL	≥126 mg/dL
Smoking status	Never or quit >12 months ago	Former or quit ≤12 months ago	Current
Diet	HEI≥69.3	HEI 56.9-69.2	HEI<56.9
Physical activity	≥150 min/wk moderate or ≥75 min/wk vigorous or ≥150 min/wk moderate+vigorous	1-149 min/wk moderate or 1-74 min/wk vigorous or 1-149 min/wk moderate+vigorous	None
Composite Score	9-14	7-8	0-6

Health-related Quality of Life will be measured by single-item linear analog scale assessments of physical, emotional, and overall health developed by members of our research team^{160,161}.

Theory-based measures. Survey items will be used to assess self-efficacy and social support for diet and physical activity that were adapted for our HIF study from instruments developed for the Patient-centered Assessment and Counseling for Exercise plus Nutrition (PACE+) program for low-income, ethnically diverse adults¹⁶² that included nutrition self efficacy¹⁶³ and social support,¹⁶⁴ physical activity self efficacy¹⁶³ and social support.¹⁶⁴ Test-retest reliabilities and internal consistency reliabilities were acceptable for all of these constructs, and association with behaviors suggested criterion-related validity^{163,164}. A 6-item measure of group social cohesion with excellent reliability (Cronbach alpha 0.95)¹⁶⁵ used in previous network intervention studies and in our pilot studies¹³⁰ will be used to assess this. Number of social contacts trying to lose weight and social norms for weight loss will be assessed using a 4-item measure with good to excellent reliability and item loadings.⁶¹

Validity concerns for survey instruments. While all scales described above to measure theory-based outcomes carry adequate validity evidence, the application of these instruments to our culturally and linguistically heterogeneous population is problematic. In the HIF project and social network analysis (see Preliminary Data), we minimized this limitation through editing of the English-language version of each item with community partners from both groups for cultural relevance, followed by forward-translation, panel discussion, backward translation, a pre-test, a cognitive briefing and consensus on the final version by a core group of community members from each group (to reflect an accurate translation and cultural appropriateness).¹⁶⁶ We have previously described this process of adapting the World Health Organization translation procedure for use with survey instruments in a CBPR framework.¹⁶⁷ We used this approach for all survey measures outlined in this proposal, and have applied them to two studies.^{103,104}

Diffusion and contamination measurement. Network interventions broadly work through social diffusion of behavior change through social networks.⁷¹ Diffusion can also be conceived as contamination if it occurs from an intervention group network into a control group network.¹⁶⁸ Indeed, randomized controlled trials of social network interventions tend to underestimate intervention effects because of contamination.^{71,169,170} To assess the potential impact of contamination on the evaluation, we will measure diffusion of content to the intervention group and control (contamination) group through methods outlined by Simmons, et al.¹⁶⁹ We will assess whether specific terminology associated with the intervention modules were recognized by network participants in both groups. Recognition of negative control terms (health promotion terms not associated with the intervention or with obesity/weight loss) will also be assessed in both groups for comparison. The difference between diffusion of intervention terms and negative control terms in both groups (intervention and control) will provide a measure of diffusion in both groups and therefore contamination in the control group.

Measurement protocol and staff training. Participants from individual social networks will be measured in the same time-frame with the HP organizing times and locations. The measurement team will consist of one or two language/culture-concordant study assistants and the study coordinator. The study assistants will be responsible for administrating the dietary recalls and the questionnaire. The study coordinator will be responsible for overseeing biometric measures.

Randomization & Sample Size Considerations

Randomization

The units of randomization will be social network subgroups. Randomization will occur after all HPs and their social network participants are enrolled and baseline measures are completed. Randomization will be stratified according to ethnicity (Hispanic or Somali), age, and sex of the HPs as well as group size.

Social network sub-groups are sufficiently discrete for randomization: Our social network data analysis determined that these communities were composed of enough discrete sub-groups for randomization. An example of this is that the Hispanic network had 144 unique sub-groups. When considering only sub-groups composed of five or more individuals, there were still 88 sub-groups identified using modularity calculations. This is a sufficient number of sub-networks for randomization, especially when considering the approximately equal number of Somali networks. Therefore, the high clustering observed in our preliminary data, as demonstrated by the high modularity of the networks, indicates that there are clearly distinct subgroups in the networks and that randomization via subgroups is feasible and appropriate for the study.

Sample size considerations

Stepped wedge cluster randomization trials typically have more statistical power than other cluster randomized designs.¹¹⁵ This is because each cluster is able to serve as its own control, accounting directly for the within cluster correlation of outcomes. In addition, the impact of intra-cluster correlation on power is typically smaller than on conventional cluster randomized trials.¹⁷¹ For the current study, we expect each HP to recruit 6 to 8 participants, so assume 7 per cluster and a substantial loss to follow up of 20% over 12 months. We assume a conservative intra-cluster correlation in outcomes of 0.10 to calculate the design effect DE_{sw} based on the formula:^{115,171}

$$DE_{sw} = \frac{1 + \rho(ktn + bn - 1)}{1 + \rho \left(\frac{1}{2}km + bn - 1 \right)} \cdot \frac{3(1 - \rho)}{2t \left(k - \frac{1}{k} \right)}$$

where $k = 2$ is the number of steps (including baseline), $b = 1$ is the number of measurements per subject in the baseline step, $t = 1$ is the number of measurements per subject at each step, and $n=7$ is the number of subjects per cluster. Assuming 80% follow up and equal

distribution across clusters, and a 80% power, we estimate the detectable standardized effects (SDs) for a range of numbers of enrolled HPs with a maximum probability of a Type II error of 0.05.

SD	HPs	N total
0.1	478	1673
0.2	120	420

0.3 53 187 For the primary endpoints, a third standard deviation (0.3SD) difference between groups will be considered clinically meaningful.¹⁷² On the basis of the previous Healthy Immigrant Families study, we will assume a 0.1 standard deviation change in the control group ("contamination") so this represents a 0.4SD change in the intervention group. Therefore, the study will accrue 54 clusters (27 per group) with approximately seven participants in each cluster, for a total sample size of approximately 378 network participants.

Data Analysis

All analyses will be appropriate for stepped wedge trials. In the direct effects model, the co-primary endpoints will be changes in BMI and waist circumference from baseline to month 12 and the 12-month change in the Ajzen TPB, the common outcome for C2DREAM. We will use mixed effects regression models to adjust for correlations within social network clusters and over time.¹¹⁴ Models will include indicators for intervention status, step, and their interaction. Covariates indicated above including demographics (e.g., sex, years since arrival to the US) and social covariates will be included in profile analysis models to assess the sensitivity of the primary analysis conditional on these potential concomitant (mediating) influences. All secondary endpoints will be analyzed using the same methods as used for the primary endpoints.

Missing data will be handled in several ways using an extensive library of macro procedures designed specifically for such tasks by the Mayo Clinic Division of Biostatistics.¹⁷³ Simple imputation methods such as minimum, average, or maximum values carried forward will be followed by multiple imputation methods to assess the robustness of the study results in the presence of the missing data. All models will be assessed for goodness of fit, with effects reported with confidence intervals. All hypothesis tests will use $\alpha = 0.05$ to determine significance.

Bibliography

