Association's "Life's Simple 7": BMI and waist circumference, blood pressure, fasting blood glucose, total cholesterol, physical activity level, and dietary quality. We will also measure quality of life and potential mediators of treatment effect consistent with our theoretical framework. The intervention will consist of community-based mentoring and education sessions, group activities, and application of a community toolkit for healthy weight loss delivered by trained HPs from Hispanic and Somali communities to their social networks. During the control period, participants will receive printed health information developed by the study team during each assessment that is not directly related to diet or weight loss.

Figure 1. Study Design and Intervention Schedule

Month	0	0	0-5	6	6-11	12	12-18	18-23	24
Intervention Group	Baseline Measures	Randomization	12 peer-led, face-to-face or virtual group-based sessions • Goal setting • Tracking of physical activity and diet • Educational content • Positive reflections	6-Month Measures	12 peer-led, face-to-face or virtual group-based sessions • Goal setting • Tracking of physical activity and diet • Positive reflections	12-Month Measures	Sustainability Phase No Organized Intervention	Sustainability Phase No Organized Intervention	24-Month Measures
			No Intervention		No intervention		12 peer-led, face-to-face or virtual group-based sessions • Goal setting • Tracking of physical activity and diet • Educational content • Positive reflections	12 peer-led, face-to-face or virtual group-based sessions • Goal setting • Tracking of physical activity and diet • Positive reflections	

Blinding. Study staff performing measurements and data analysis as well as all named investigators will be blinded to treatment condition.

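### A handout described only for the control period is given during the month-6 and month-12 visits, and can reveal the arm to measurers the plan calls blinded; a shared staff role is a lesser route

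*Combined protocol and SAP*

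**What the plan says.** The Blinding paragraph under Study Design and Procedures states: "Study staff performing measurements and data analysis as well as all named investigators will be blinded to treatment condition". The Measures section repeats that data at 0, 6, 12 and 24 months are gathered "by trained study staff blinded to treatment condition", and marks month 12 as the primary endpoint.

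The Overview paragraph describes what participants get while waiting: "During the control period, participants will receive printed health information developed by the study team during each assessment". The content is described as not bearing directly on diet or weight loss.

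Measurement protocol and staff training sets out the field team: "The measurement team will consist of one or two language/culture-concordant study assistants and the study coordinator". Duties follow: "The study assistants will be responsible for administrating the dietary recalls and the questionnaire", and "The study coordinator will be responsible for overseeing biometric measures".

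Under Treatment Fidelity, study assistants "will randomly observe 5% of sessions with the HPs". The same section adds: "Bi-weekly meetings will be held with the HPs and study team to reinforce treatment fidelity".

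The documents describe no printed material for the intervention arm. They do not say who hands out the control-period material, or at what point in the visit. They do not say whether a session observer may later collect outcomes from the same network.

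**The concern.** The blinding statement is unqualified, but the visit as described contains an item that only one arm receives. A measurer who sees it, or hands it out, learns the network's assignment.

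This matters most for waist circumference, a co-primary that depends on where the tape is placed and how it is read. A small, unintended tendency in one direction by arm would enter the month-12 comparison directly and would not average out.

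A second, weaker route concerns the outcomes collected by study assistants. Anyone who has watched a session before month 12 knows that the network is in the immediate arm. The same job title is responsible for the recalls and questionnaire, which supply the diet and physical activity components of the secondary Life's Simple 7 score.

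**Working it through.** No power or alpha figure is involved, so the check sets the provisions side by side.

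**Step 1: when the handout separates the arms.** Inputs are the Randomization section (assignment after baseline measures), the Overview (delay of one year) and Figure 1 (session schedule).

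| Visit | Immediate arm | Delayed arm | Handout as described |
|---|---|---|---|
| Baseline | not yet assigned | not yet assigned | cannot signal arm |
| Month 6 | in intervention | control period | delayed arm only |
| Month 12 (primary endpoint) | 12 + 12 = 24 sessions scheduled by then | control period, sessions not begun | delayed arm only |
| Month 24 | no organized intervention | control period over | neither arm |

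The signal is confined to months 6 and 12.

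**Step 2: who could see it.** The material is given at the assessment itself, and the team is one or two assistants plus the coordinator. In so small a team an item given during the visit can come to the notice of any member, including whoever measures waist. The plan says that the coordinator oversees biometric measures. It does not say who holds the tape.

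**Step 3: which primary measures are open to influence.** Under Primary outcome measures:
- BMI: height is taken at baseline only, before assignment. Change in BMI therefore rests on weight from a digital floor scale, which leaves little room for judgement.
- Waist: two manual readings are taken, with a third if they differ by more than 2.0 cm, and the two closest are averaged. This controls disagreement between readings. It does not detect a shift common to both. For scale only, the pilot's mean change was 102.3 − 100.6 = 1.7 cm (Table 2), which is smaller than that tolerance. This is not an estimate of bias.

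**Step 4: the observer route.** Figure 1 shows no sessions in the delayed arm before month 12, so every session observed by then belongs to an immediate-arm network. Observation and recall/questionnaire collection are both assigned to study assistants.
- Recalls are self-administered under supervision in English or Spanish. For other languages, a staff member and an interpreter complete them with the participant (Dietary Quality), so staff influence is greater there.
- Data Analysis lists the 12-month Ajzen TPB change with the co-primaries but does not say how it is collected. If it is part of the questionnaire, it shares this exposure.
- No section assigns assistants to BMI or waist, or has the coordinator observe sessions. The route is documented only for recall and questionnaire outcomes.

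**Step 5: safeguards.** The blinding statements themselves prohibit an assessor from knowing the arm. No procedure is described for achieving this on either route.

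**The case against.** The strongest reply is that nothing here contradicts the blinding statement. That statement is itself a rule: someone who knows a network's arm and then measures it would breach the plan. A handout given at the end of the visit by someone else would fit the text. This stands as far as it goes, and a reader who infers that assessors *are* unblinded goes beyond the documents. But the plan can be followed as written with the handout given before the tape is used, and nothing directs staff otherwise.

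A reader might also infer that session observers go on to measure BMI and waist. The documents do not support this, because assistants are assigned the recalls and questionnaire and the coordinator oversees biometrics. Overlap of observer and collector is at the level of the job title, not a named person. It can be argued that observers are a separate subset, those who were interventionists in the earlier family study. However, that clause reads as a description of the assistants rather than a restriction, so it does not establish separation.

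Counting how many networks would have an observed session might seem to size the problem. It would not: the relevant quantity is how often an assessor knows the arm of a network being assessed, and that depends on staffing that the plan does not give.

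Finally, participants know their own arm and meet assessors face to face. Self-report bias therefore exists whatever assessors know. That is correct, and it limits what any fix can achieve. It does not justify adding an avoidable signal at the primary-endpoint visit.

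**Conclusion.** The point holds as a gap between an unqualified blinding claim and a procedure that can defeat it at months 6 and 12. The handout is the main route, and waist circumference is the co-primary at risk. BMI change is less exposed. The observer route is secondary and is documented only for recall and questionnaire outcomes.

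The conclusion rests on two readings. The first is that the immediate arm receives no matching material, since none is described. The second is that giving the handout at the assessment brings it within the field team's sight. The documents do not settle who distributes it or when.

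The size of any bias cannot be estimated. This should be corrected because the main remedy costs almost nothing, but it does not show that the trial's results would be biased.

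**What to change.** 1. Give the same printed material, unrelated to diet or weight loss, to both arms at every visit; or hand it out only after all measures for that visit are recorded. State who distributes it. Matching material is the cleaner option: an end-of-visit handout at month 6 could still inform a team member who returns at month 12.
2. Where existing staffing allows, do not assign an assistant who observed a network's session to collect that network's month-6 or month-12 outcomes. Where it does not, describe assessor blinding as partial for the outcomes that assistant collects.
3. State who measures waist circumference and how the Ajzen TPB is collected.
4. Qualify the blinding statement by acknowledging the routes that remain: visits organized by Health Promoters, bi-weekly meetings between Health Promoters and the study team, intervention-term recognition items asked in both groups, and participants who know their arm.

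The cost is a little printing or a changed visit order, some added text, and a scheduling constraint that may not always be workable if there are few assistants per language.
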